9.8 Pregnancy Reporting

Pregnancies detected in subjects assigned to study drug should be promptly reported to Product Safety within 24 hours of awareness via fax, using the Pregnancy Notification Form. If a female patient becomes pregnant following assignment to study treatment, the study product will be immediately discontinued and the patient will be followed until the outcome of the pregnancy is known.

Product Safety should be notified promptly via fax of any updates on the status of the pregnancy by update and/or amendment of the initial pregnancy notification form.

Although pregnancy occurring in a clinical study is not considered to be an AE or SAE, any pregnancy complication (i.e. spontaneous abortion) or elective termination of a pregnancy, for medical reasons, will be recorded as an AE or SAE and followed as such.

9.10 Regulatory Reporting Requirements for SAEs

The investigator, or responsible person per local requirements, must comply with the applicable local regulatory requirements related to the reporting of SAEs and IND safety reports to regulatory authorities and their IRB/EC.

Amendment 5: 28 Mar 2016

10 STUDY ACTIVITIES

The study Schedule of Assessments is provided as Appendix 2, and the Specialty PK and PD Laboratory Testing Schedule is provided as Appendix 3.

10.1 Visit 1: Screening (Days -21 to -1)

Study specific screening procedures will begin only after the informed consent form (ICF) has been signed and the consent process conducted with the patient has been briefly described in the patient's source documents. The Screening Period will be scheduled to conduct procedures that confirm the patient is fully eligible for the study. Screening for the inclusion/exclusion criteria will occur within 3 weeks before study drug administration.

The following procedures will be performed during Screening:

- Obtain informed consent
- Evaluate inclusion and exclusion criteria
- Record patient demographics, medical history, and vital signs
- Record medication history (prescription and over the counter [OTC]) during the 8 weeks before Screening
- Record RA history and prior RA treatment(s)
- Perform a 12-lead ECG
- Perform a chest X-ray (Note: a chest X-ray is not required if a chest X-ray with no clinically significant findings was performed within 1 month of randomization)
- Perform a physical examination
- Perform a serum pregnancy test for all females of childbearing potential
- Collect blood samples on a day during Screening when the patient has fasted for 4 to 6 hours for:
 - Complete blood count with differential and platelet count (CBC) and chemistry
 - CRP
 - HCV antibody, HIV antibody, HBsAg, and QFT
 - RF and ACPA
 - ESR (done at site with the kit provided)
- Collect urine sample for urinalysis
- Inform patients of the study restrictions outlined in the inclusion/exclusion criteria
- Conduct the DAS28-CRP and ACR Core Set Measurements
- Complete the HAQ-DI

10.2 Treatment Period (Days 1 to 43)

The once-weekly visits during the Treatment and Follow-up Periods can be scheduled for ± 2 days around each of the designated Days in this schedule, but the designated Days themselves will not be shifted relative to Day 1.

Amendment 5: 28 Mar 2016

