Figure 2 provides a study schematic indicating visit structure for each individual cohort. After initial Screening, eligible patients will return to the study site at weekly intervals throughout the Treatment Period for study drug administration and safety, PK, PD, efficacy, and other assessments. Enrolled patients will also return to the study site between study drug administration visits for the assessment of PK/PD endpoints. Primary and secondary efficacy endpoints will be assessed at the End-of-Treatment Visit on Day 43. During the 4-week Follow-up Period, patients will return to the study site at 2 weeks and 4 weeks after the end of the Treatment Period for additional assessments.

Santarus, Inc.
SAN-300
Confidential
Clinical Trial Protocol: C2013-0302

Amendment 5: 28 Mar 2016

Figure 1. Study Design for Study C2013-0302

Abbreviation: PBO = placebo; QW = every week; QOW = every other week.

Notes: Patients will be randomized to each cohort in a 3:1 ratio of SAN-300 to placebo. A Safety Committee Review will occur after patients have completed the 6-week Treatment Period of each cohort. Any subject who withdraws prior to the end of the 6-week Treatment Period will not be replaced and the Study Safety Committee will review the data from all subjects regardless of duration of participation in the study.

Randomization Primary Efficacy Endpoint Last Visit Screening Treatment Period Follow-up Period SAN-300 SC (N=30) Screening Period Placebo SC (N=10) Visit: 1 2 3 4 5 6 7 8 9 10 Dav: -21 1 8 15 22 29 36 43 57 71 Week: 1 7 11

Last weekly SAN-300 dose

Last every-other-week SAN-300 dose

Figure 2. Study Design for Individual Cohorts

Abbreviation: SC = subcutaneously.

Screening: Between Days -21 and -1. Informed consent will be obtained before any study specific procedures are performed. Eligibility assessments will be performed.

Treatment Period: Days 1 to 43. Baseline assessments and measurements will be performed before dosing with study drug. Patients will receive SC injections of study drug as follows:

- For all cohorts, patients randomized to receive placebo will be administered a total of six once-weekly injections of placebo on Days 1, 8, 15, 22, 29, and 36.
- In Cohorts A, B, E and F, patients randomized to receive SAN-300 will be administered a total of six weekly injections of SAN-300 on Days 1, 8, 15, 22, 29, and 36.

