3.2 Rationale for Study Design and Control Group

3.2.1 Rationale for Dosing Regimen

The planned doses (0.5 mg/kg once weekly through 4.0 mg/kg every week) and duration of study treatment are based on the observed safety, PK, and PD profile of SAN-300 (including VLA-1 receptor occupancy) in Phase 1 single-dose Study 301 and data from up to 3 months of dosing in non-human primate studies (Section 1.2.3). Based on receptor occupancy data, SAN-300 2.0 mg/kg SC resulted in durable VLA-1 receptor occupancy through Day 8 and the 4.0 mg/kg SC dose extended this receptor occupancy through approximately Day 15. These results suggest that weekly or every-other-week dosing may be sufficient to maintain a therapeutic effect.

In Study 301, single doses of SAN-300 up to 6.0 mg/kg SC were tolerated in a healthy volunteer population. To ensure patient safety, the design of the current multiple ascending dose study stipulates a Safety Review to occur after each dosing Cohort. The overall drug exposure in each cohort is as follows:

Table 1 Overall Study Drug Exposure by Cohort

Cohort	SAN-300 Dose Regimen	Overall Exposure
A	0.5 mg/kg QW	3.0 mg/kg
В	1.0 mg/kg QW	6.0 mg/kg
С	2.0 mg/kg QOW	6.0 mg/kg
D	4.0 mg/kg QOW	12.0 mg/kg
E	4.0 mg/kg QW	24.0 mg/kg
F	2.0 mg/kg QW	12.0 mg/kg

Abbreviations: QOW = every other week; QW = every week

Both weekly and every-other-week dosing will be explored to investigate appropriate dosing parameters for SAN-300. Should every-other-week dosing be a viable option for treatment of patients with RA, this dosing regimen would decrease patient burden.

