5 TREATMENTS TO BE ADMINISTERED

5.1 Planned Dose Cohorts

Eligible patients will be enrolled into a dose cohort and randomized (3:1) to receive either SAN-300 via SC injection over 6 weeks or a matching volume of placebo. More than one SC injection may be required (maximum volume of 1.2 mL per SC injection) depending on the total dose administered and the weight of the individual patient. Dosing by cohort is provided in Table 2.

Table 2. Dose Cohorts for Study C2013-0302

	Number of Patients to be Dosed		
Cohort	SAN-300	Placebo	SAN-300 Dose
А	6	2	0.5 mg/kg SC once weekly
В	6	2	1.0 mg/kg SC once weekly
С	6	2	2.0 mg/kg SC every other week
D	6	2	4.0 mg/kg SC every other week
Е	6	2	4.0 mg/kg SC once weekly
F	6	2	2.0 mg/kg SC once weekly

Abbreviations: SC = subcutaneous

Safety and tolerability findings will be reviewed in a blinded manner for all patients in a cohort after the 6-week Treatment Period to determine whether or not enrollment will begin in the next cohort. Any subject who withdraws prior to the end of the 6-week Treatment Period will not be replaced and the Study Safety Committee will review the data from all subjects regardless of duration of participation in the study. The safety review will include, at minimum, the following information: AEs; safety laboratory results; vital sign measurements; and reasons for premature study withdrawal.

The decision to begin enrollment in the next cohort will be based upon the results of the safety review. In addition, based on the findings of the Study Safety Committee, the Sponsor may elect to modify the dose in the next cohort to a lower dose or terminate any further dose escalation.

Refer to Section 3.4 for patient and study stopping rules.

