Other Assessments		.		L	L	 		 		L	· L		.4
RF, ACPA	Х										Х		
ANA		Х									Х		

Abbreviations: ACPA = anti-citrunillated peptide antibodies; ACR = American College of Rheumatology; ANA = antinuclear antibody; aPTT = activated partial thromboplastin time; CBC = complete blood count with differential and platelet count; CCP = cyclic citrullinated peptide; DAS28-CRP = Disease Activity Score with 28-joint count C-reactive protein; ECG = electrocardiogram; ESR = erythrocyte sedimentation rate; HAQ-DI = Health Assessment Questionnaire – Disease Index; HBsAg = hepatitis B surface antigen; HCV = hepatitis C virus; HIV = human immunodeficiency virus; CRP = C reactive protein; INR = international normalized ratio; MRI = magnetic resonance imaging; PT = prothrombin time; QFT = QuantiFERON®-TB Gold test; RA = rheumatoid arthritis; RF = rheumatoid factor; UA = urinalysis.

Weekly visits during the Treatment and Follow-up Periods can be scheduled for ±2 days around each of the designated Days in this schedule, but the designated Days themselves will not be shifted relative to Day 1.

b If a chest X-ray was performed with no clinically significant findings within 1 month of randomization, another chest X-ray is not required at Screening.

Santarus, Inc. SAN-300

Amendment 5: 28 Mar 2016

CONFIDENTIAL Clinical Trial Protocol: C2013-0302

Page 65 of 118

For all cohorts, patients randomized to receive placebo will be administered a total of 6 once-weekly SC injections of placebo on Days 1, 8, 15, 22, 29, and 36. In Cohorts A, B, and D, patients randomized to receive SAN-300 will be administered a total of 6 once-weekly SC injections of SAN-300 on Days 1, 8, 15, 22, 29, and 36. In Cohorts C and E, patients randomized to receive SAN-300 will be administered a total of three every-other-week SC injections of SAN-300 on Days 1, 15, and 29 and will be administered a total of three every-other-week SC injections of placebo on Days 8, 22, and 36. Note: Subject to be observed at minimum 1 hour post- dose. Longer observation allowed if deemed necessary by investigator or designee.

- d Day 1 dosing will occur on the day of or within 24 hours after randomization.
- ^e After baseline assessment, additional assessments of tryptase and histamine to occur only in suspected cases of anaphylaxis or hypersensitivity reactions.

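### The ±2-day window applies to each dosing visit separately, so in-window injections from the second dose on can be 3 to 11 days apart in weekly arms and 10 to 18 in every-other-week arms, in conflict with the stated regimens

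*Protocol*

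**What the plan says.** Protocol Section 10.2 sets a tolerance for the dosing and follow-up visits: they "can be scheduled for ± 2 days around each of the designated Days in this schedule". It then anchors the targets to the start of dosing, so that an early or late visit does not move the next target: "but the designated Days themselves will not be shifted relative to Day 1". Footnote a of protocol Appendix 2 repeats this ("Weekly visits during the Treatment and Follow-up Periods can be scheduled for ±2 days around each of the designated Days in this schedule"), and so does footnote a of SAP Appendix 1.

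The injections are given at these visits: Sections 10.2.3 and 10.2.5 list study drug administration among the procedures for Visits 3 to 7.

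The regimens are defined by frequency. Section 3.1 has patients "return to the study site at weekly intervals throughout the Treatment Period for study drug administration". In the weekly cohorts it specifies a "total of six weekly injections of SAN-300 on Days 1, 8, 15, 22, 29, and 36". In the every-other-week cohorts SAN-300 is given on Days 1, 15 and 29, with placebo on the other weeks. Tables 1 and 2 name each arm by dose and interval, the most intensive being "4.0 mg/kg SC once weekly" (Cohort E).

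I found no statement in either document of a minimum or maximum interval between consecutive injections.

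**The concern.** The target days do not move when a visit is early or late. A late dose therefore does not push back the next window, and the two tolerances add. A tolerance of 2 days on each visit becomes 4 days on the interval, which is large against a 7-day regimen.

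Two things are at stake. The first is safety in a repeat-dose study whose primary objective is safety and tolerability. Within the window, the highest-intensity arm can receive consecutive doses much closer together than its label says. Blood counts are drawn at the dosing visits and analysed centrally, and individual dosing stops on a confirmed neutrophil reduction, so a short gap leaves less time to act on a result before the next injection.

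The second is interpretation. The arms differ by interval as well as dose, and tolerability, receptor occupancy and PK will be read by regimen. If actual intervals vary widely and are not reported, the regimen labels may not describe what patients received.

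**Working it through.** **Inputs.** Weekly dosing days 1, 8, 15, 22, 29, 36; every-other-week SAN-300 days 1, 15, 29 (Section 3.1). Window ±2 days around fixed days (Section 10.2). Doses from Table 2. Day 1 is the anchor and has no window.

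**The plan's own figure.** Table 1 exposure = dose × number of SAN-300 injections: A 0.5 × 6 = 3.0; B 1.0 × 6 = 6.0; C 2.0 × 3 = 6.0; D 4.0 × 3 = 12.0; E 4.0 × 6 = 24.0; F 2.0 × 6 = 12.0 mg/kg. All six rows reproduce. These totals count injections and do not depend on the spacing.

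**Allowed gaps.** For two windowed doses on target days a and b, the shortest gap is (b − 2) − (a + 2) and the longest is (b + 2) − (a − 2).

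| Gap | Nominal (days) | Shortest (days) | Longest (days) |
|---|---|---|---|
| Weekly, doses 1 to 2 | 7 | 6 − 1 = 5 | 10 − 1 = 9 |
| Weekly, each later pair (e.g. Days 8 and 15) | 7 | 13 − 10 = 3 | 17 − 6 = 11 |
| Every other week, SAN-300 doses 1 to 2 | 14 | 13 − 1 = 12 | 17 − 1 = 16 |
| Every other week, SAN-300 doses 2 to 3 | 14 | 27 − 17 = 10 | 31 − 13 = 18 |

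Enumerating every combination of offsets gives the same ranges. The swing of 4 days is 4/7 = 57% of the weekly interval and 4/14 = 29% of the every-other-week interval. If the first injection uses the 24-hour allowance in Section 10.2.1 and later days still count from randomization, the first weekly gap can be 6 − 2 = 4 days.

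**How far it can go in one patient.** At most two 3-day gaps can occur. Three consecutive injections need at least (22 − 2) − (8 + 2) = 10 days, against 14 nominal. The between-dose PK visits do not prevent a short gap: doses on Days 24 and 27 have no scheduled visit between them.

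**Cohort E.** Two doses total 2 × 4.0 = 8.0 mg/kg, allowed over 3 days instead of 7. Two doses in the other weekly cohorts total 1.0 (A), 2.0 (B) and 4.0 (F) mg/kg.

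**Would the SAP show it?** SAP Section 8.1 defines extent of exposure as last dose minus first dose plus one. Compare two Cohort E patients:
- Days 1, 8, 15, 22, 29, 36: gaps 7, 7, 7, 7, 7
- Days 1, 10, 13, 24, 27, 36: gaps 9, 3, 11, 3, 9

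Both have 36 − 1 + 1 = 36 days of exposure, six doses and 24.0 mg/kg, so the planned summary cannot tell them apart. SAP Section 4.2 lists all protocol deviations, but a gap made of two in-window visits may not be recorded as one. Listing 16.2.5.1 covers drug exposure by subject, but no interval summary is promised.

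**The case against.** A tolerance around a nominal schedule is ordinary and does not in itself contradict the schedule. The fixed days bound every gap and stop cumulative drift. A 3-day gap needs a visit as late as allowed followed by one as early as allowed, and nothing in the documents says how often that would happen. Blood counts, adverse event collection and stopping rules apply whatever the gap, and population PK modelling can use actual dose times. All of this stands. What is missing is an explicit interval rule, not every bound. One can also argue that Section 3.1 still requires weekly dosing, so a 3-day gap is not compliant. That reading only shows that the two passages give a site different answers.

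Three stronger readings are tempting and are not supported:

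- *Two Cohort E doses 3 days apart breach the tolerated dose.* Section 3.2.1 says that "single doses of SAN-300 up to 6.0 mg/kg SC were tolerated in a healthy volunteer population". That is a single-dose observation, not a ceiling on summed repeat doses, and the nominal schedule already gives 8.0 mg/kg on two days a week apart. As an illustration only, take one-compartment decay, no absorption phase, and the monkey half-lives in Section 1.2.2 (38.4 to 154 hours). The load just after the second dose is 4.0 × (1 + 0.5^(t/half-life)). At t = 72 hours it is 5.1 to 6.9 mg/kg; at t = 168 hours it is 4.2 to 5.9. It reaches 6.0 at 3 days only when the half-life is 72 hours or more. At 154 hours, six nominal weekly doses also accumulate to 7.5. The documents cannot settle the comparison.
- *The dose rationale covers no short-interval dosing.* Section 3.2.1 also relies on primate data, and Section 1.2.3 describes twice-weekly dosing for 3 months at up to 20 mg/kg. That study set no NOAEL, so it does not establish safety either.
- *An 11-day gap is wrong because it outlasts the Day 8 occupancy cited for 2.0 mg/kg.* Cohort C deliberately gives 2.0 mg/kg every 14 days, so going past Day 8 is part of the design.

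**Conclusion.** The concern holds as a conflict between a stated visit rule and the stated regimens, together with a gap in the planned reporting. Within the window, weekly injections from the second dose onward may be 3 to 11 days apart (first gap 5 to 9), and the second and third SAN-300 doses in the every-other-week arms 10 to 18 days apart. It matters most at 4.0 mg/kg weekly. It does not establish harm, an exceeded exposure limit or a changed total dose.

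The ranges assume that each visit uses its window independently, that the injection is given on the visit day, and that Day 1 is the first dose. They describe what the text permits; no frequency is claimed.

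**What to change.** 1. Reconcile the window in protocol Section 10.2, footnote a of protocol Appendix 2 and footnote a of SAP Appendix 1 with the regimens in Sections 3.1 and 3.2.1 (Table 1) and in Table 2. The sponsor's clinical team should state whether an interval requirement between injections applies; no value is proposed here.
2. In the same edit, reconcile footnote c of both appendices. It makes Cohort D weekly and Cohort E every other week, contrary to Section 3.1 and Table 2, and does not mention Cohort F.
3. Add to SAP Section 8.1 a summary of actual between-injection intervals by cohort, using SAN-300 doses for active patients in Cohorts C and D, and a listing of departures from the nominal interval. SAP Section 3.5 already reports 41 subjects randomized, so this is the part that remains fully actionable.

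The cost is a sentence in each of the three places, one summary and one listing, and slightly less scheduling freedom for sites if a requirement is stated.

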10.2.1 Visit 2 (Day 1) Procedures

Eligible patients will return to the study site for enrollment, randomization, and administration of the first dose of study drug. Patients should arrive at the study site having fasted for 4 to 6 hours. The following procedures will be performed at Visit 2:

Before Randomization:

- Review inclusion and exclusion criteria and medical history
- Record all AEs since previous visit
- Record all medications (prescription and OTC) taken by the patient since Screening
- Record RA history and prior RA treatment(s)
- Record vital signs
- Perform a urine pregnancy test for all females of childbearing potential
- Collect urine for urinalysis
- MRI of the hand and wrist most clinically affected by RA (to occur within 5 days before or at Visit 2) should be performed on patients able to tolerate the MRI procedure.

Randomize the patient via the IVRS/IWRS system.

After Randomization but before Study Drug Administration:

- Collect blood samples for:
 - CBC and chemistry
 - ESR (done at site with the kit provided)
 - International normalized ratio (INR), prothrombin time (PT), activated partial thromboplastin time (aPTT)
 - Tryptase and histamine
 - Complement (C3, C4, and CH50)
 - CRP concentration
 - Serum immunoglobulins
 - ANA
 - Anti-SAN-300 antibodies
 - Serum SAN-300 concentration
 - Cytokine assessments (IFN_γ, TNFα, IL-6)
 - Immunophenotyping panel (CD3/CD14/CD45RO/CD49a/CD45/CD4/CD19/CD8)
 - VLA-1 receptor occupancy
- Conduct the DAS28-CRP and ACR Core Set Measurements
- Complete the HAQ-DI

Administer study drug according to the randomization of the patient. Day 1 study drug administration should occur on the day of or within 24 hours after randomization.

After Study Drug Administration:

 Observe subject at minimum 1 hour post dose. Longer observation allowed if deemed necessary by investigator or designee.

Amendment 5: 28 Mar 2016

 Record blood pressure and pulse at the end of the 1 hour observation period prior to the blood sample collection

- Collect blood sample at 1 hour post dose for serum SAN-300 concentration
- Collect AEs since study drug administration

10.2.2 Visit 2A (between Days 2 to 4) and Visit 2B (between Days 5 to 7)

Patients will come to the study site at a random, scheduled time within each of these intervals to have blood samples collected for serum SAN-300 concentration and VLA-1 receptor occupancy.

Record all AEs and medications taken since previous visit

10.2.3 Visits 3, 4, and 5 (Days 8, 15, and 22) Procedures

Patients should arrive at the study site having fasted for 4 to 6 hours. The following procedures will be performed at Visits 3 to 5:

- Record all medications (prescription and OTC) taken by the patient since previous visit
- Record all AEs since previous visit
- Record vital signs
- Perform a urine pregnancy test for all females of childbearing potential (Visit 5 only)
- Collect blood samples for:
 - CBC and chemistry
 - ESR (done at site with the kit provided)
 - CRP concentration
 - Anti-SAN-300 antibodies (Visit 3 only)
 - Serum SAN-300 concentration
 - Cytokine assessments (IFN_γ, TNFα, IL-6) (Visit 3 only)
 - Immunophenotyping panel (CD3/CD14/CD45RO/CD49a/CD45/CD4/CD19/CD8) (Visits 3 and 4 only)
 - VLA-1 receptor occupancy (Visits 3 and 4 only)
- Conduct the DAS28-CRP and ACR Core Set Measurements
- Administer the study drug appropriate to the randomization of the patient
- Complete the HAQ-DI
- Observe subject at minimum 1 hour post dose. Longer observation allowed if deemed necessary by investigator or designee
- Record blood pressure and pulse at the end of the 1 hour observation period
- Collect AEs since study drug administration

10.2.4 Visit 3A (between Days 9 to 11)

Patients will come to the study site at a random, scheduled time within this interval to have a blood sample collected for serum SAN-300 concentration.

Record all AEs and medications taken since previous visit

Amendment 5: 28 Mar 2016

